The final question in this section relates to sharing de-identified "free text" data for research.

Here is the table of de-identified health care data you saw earlier, but this time a column labelled "Notes" has been added. This is known as "free text" data.

Research ID	Age	Sex	Region	Diagnoses	Notes
5X62V	69	М	Kent	pneumonia high blood pressure	1 st April 2019. XXX has a fever and cough. His chest sounds crackly. I think he has pneumonia. Sent to hospital.
597PT	24	F	Dundee	depression carpal tunnel syndrome	2 nd April 2019. XXX rates her mood as 1/10 on average, she is more tired, and she is not looking forward to anything. Her depression has worsened. She wishes to restart citalopram.
8HG7S	89	F	Glamorganshire	broken humerus anxiety	3 rd April 2019. XXX fell after skidding on an oily patch while cycling and was hit by a car. She has an obvious fracture of her left upper arm. She needs an X-ray.
BA6A9	45	м	London	schizophrenia diabetes	4 th April 2019. XXX still worries that other people can hear his thoughts, but this is getting less common. He is attending cognitive-behavioural therapy sessions.

Like the last example the data remains de-identified but gives the researchers more information. As there is more information there is a slightly increased risk of someone being identified from the data.

For example, in the table above, an "89-year-old cyclist skidding on oil and being hit by a car" may be reported in a local newspaper. Whilst the lady is not named in the data above, she would almost

certainly be named in the newspaper and it may therefore be possible for researchers to work out who she is.

Q9

How likely would you be to share your FREE TEXT de-identified PHYSICAL health data with the following, without giving consent every time:

Physical Health	Very Likely	Likely	Not Sure	Unlikely	Very Unlikely	Prefer not to say
Any part of the NHS doing research						,
Academic institutions doing research (e.g. universities)						
A national charity doing research (e.g.						
MIND, Cancer Research UK, British Heart						
Foundation)						
A profit-making company doing research						
into treatments (e.g. a pharmaceutical						
company, health technology company)						
A profit-making company doing other						
research (e.g. an insurance company,						
broadband provider)						
Publicly						

Q10

How likely would you be to share your FREE TEXT de-identified MENTAL health data with the following, without giving consent every time:

Mental Health	Very	Likely	Not	Unlikely	Very	Prefer
	Likely		Sure		Unlikely	not to
						say
Any part of the NHS doing research						
Academic institutions doing research (e.g.						
universities)						
A national charity doing research (e.g.						
MIND, Cancer Research UK, British Heart						
Foundation)						
A profit-making company doing research						
into treatments (e.g. a pharmaceutical						
company, health technology company)						
A profit-making company doing other						
research (e.g. an insurance company,						
broadband provider)						
Publicly						

On a slightly different topic....

Imagine that there was a single place where you could securely sign up to choose how your NHS identifiable health data is used.

This would cover how your confidential patient information is managed across all UK NHS services, and how your NHS de-identified data could (or could not) be used for research.

It would be in the form of a standardised UK-wide CONSENT FORM that all NHS services could use.

Q11

How likely would you be to sign up if you were asked to sign:

	Very	Likely	Not	Unlikely	Very	Prefer
	Likely		Sure		Unlikely	not to
						say
Online (via a website)						
By downloading an app (e.g. the NHS App)						
On paper forms available from pharmacies,						
the Post Office, etc. (and sent by post)						
In person (e.g. when attending your GP, at a						
hospital clinic, etc.)						

Q12

Would you be likely to sign up if your consent form were then stored and managed securely by the following institutions?

	Very	Likely	Not	Unlikely	Very	Prefer
	Likely		Sure		Unlikely	not to say
Centrally by NHS England/NHS						
Scotland/NHS Wales/HSC Northern						
Ireland						
Your local NHS Trust						
Your GP						

Q13

If you wanted to change your preferences, how likely would you be to use the following methods?

	Very	Likely	Not	Unlikely	Very	Prefer
	Likely		Sure		Unlikely	not to
						say
Online (via a website)						
By downloading an app (e.g. the NHS App)						
On paper forms available from pharmacies,						
the Post Office, etc. (and sent by post)						
In person (e.g. when attending your GP, at a						
hospital clinic, etc.)						

Q14 Assume that you were able to sign up and change your choices in a way you preferred, and that the consent form was stored securely in a place where you felt comfortable.

How likely would you be to use this system to choose how your NHS health data is managed?

	Very Likely	Likely	Not Sure	Unlikely	Very Unlikely	Prefer not to
	- /				/	say
Overall likelihood that you would sign						
up						

The last part of the survey (before we ask a few questions to ensure we have reached a broad section of the UK) examines what a consent form to share our health data could look like. By completing one consent form it would then be possible for all UK NHS professionals to access their patient's identifiable health data for their clinical care, saving time for both patients and health care professionals.

Please take a look at the consent form below:

Q15

Having looked at the consent form, please agree or disagree with the following statements.

(If you would like to take another look at the consent form at any time while answering this question, you can use the 'previous' button at the bottom of this page to look back. This will not affect answers already given.)

	Strongly Agree	Agree	Neither Agree nor Disagree	Disagree	Strongly Disagree	Prefer not to say
The consent form is easy to read.						
The consent form is clear and easy to						
understand.						
The statements (in blue) help me to						
understand what I am consenting to.						
The consent form is clear that my						
identifiable health data would only be						
used by appropriate NHS health care						
professionals.						
I understand the term 'NHS-approved						
researchers' and which individuals this						
may refer to.						
The consent form makes clear that it						
would be used for my preferences						
about sharing my IDENTIFIABLE health						
data within the NHS for my CLINICAL						
CARE.						
The consent form makes clear that it						
would also be used for my preferences						
about sharing my DE-IDENTIFIED health						
data for RESEARCH purposes.						
I would like the consent form to give						
specific options about how researchers						
can contact me (e.g. by post only, e-						
mail).						
I would like to see a statement added						
about the security of data sharing.						
I would like to see a statement added						
about where my consent preferences						
will be stored.						
Before seeing this consent form, I was						
aware of the NHS National Data Opt-						
Out.						
The consent form reassures me that my						
identifiable health data is safe in the						
NHS.						
If this consent form were put in front of						
me today, I would sign it.						

If you would like to make any comments about the consent form, please do so here:

There are currently many individual websites where people can sign up to take part in research. Examples include charity websites, the national "Join Dementia Research" register, and the National Institute for Health Research (NIHR) "be part of research" campaign.

Q16

An alternative might be a national sign-up portal, on a web site, where people could register their preferences about taking part in all NHS research.

Choose the statement you agree with most:

- Everything is fine as it is; leave it to individuals to sign up with the various organisations.
- Have two national NHS research websites, one where people can sign up for mental health research, and a second website where people can sign up for physical health research.
- Have a national NHS research website where people can sign up for all conditions.
- Not sure.

Q17

Finally, it can be very valuable for research to link health (NHS) data to other data sources.

For example, causes of death (from death certificates) are held by the UK Office of National Statistics (ONS), rather than the NHS -- so to find out more about the reasons people die, NHS and ONS data must be linked.

Usually, this is done as follows:

a) Research teams seek special permission for the process.

b) The relevant information from each organization, plus a small amount of identifiable information, is given to a "trusted third party" (e.g. an NHS Trust, the Office of National Statistics).

c) The trusted third party links the information, then removes any details that can identify anyone.

d) Researchers are then given access to the de-identified information only, under special controls.

We are interested to hear whether you would be happy for your health data to be linked, in this way, to:

	Yes	Not sure	No	Prefer not
				to say
Educational data (e.g. to study impact of illness on				
education)				
Police/Criminal Justice data (e.g. to study health in the				
victims of crime)				
Transport/DVLA data (e.g. to study health and				
pollution)				
Housing data (e.g. impact of social housing on health)				
Immigration data (e.g. health in immigrants)				
Social security/Work and Pensions (e.g. to study				
health and financial insecurity)				

Data held about you for research by universities (e.g.		
if you have volunteered for research studies)		
Data held about you by private companies		

Demographics

And finally, to ensure we have surveyed a wide range of the population (please note, all questions have a "prefer not to say" option and have been written to apply to all of the home nations):

Do you consider yourself to be:

- Prefer not to say
- Female
- Male
- Prefer to self-describe (please specify)

May we know which age range you fit in?

- Prefer not to say
- Under 12
- 12-17
- 18-24
- 25-34
- 35-44
- 45-54
- 55-64
- 65-74
- 75-84
- 85+

What do you consider your ethnicity to be?

- Prefer not to say
- White
- Irish Traveller
- Mixed/Multiple ethnic groups
- Asian or Asian British
- Indian
- Pakistani
- Bangladeshi
- Chinese
- Black/African/Caribbean/Black British
- Arab
- Other ethnic group or prefer to self-describe (please specify)

What is the highest qualification you have achieved?

• Prefer not to say

- No formal qualifications
- Secondary school level qualifications e.g. CSE, GCSE, O-Levels, Nationals, or equivalent
- A-Levels, Highers, or equivalent
- Vocational qualification or equivalent
- Undergraduate degree or equivalent
- Postgraduate or professional qualification or equivalent

Do you consider yourself to be

- Prefer not to say
- Heterosexual (straight)
- Homosexual (gay or lesbian)
- Bisexual
- Other or prefer to self-describe (Please specify)

What is your religion if any?

- Prefer not to say
- No religion
- Christian
- Muslim
- Hindu
- Sikh
- Jewish
- Buddhist
- Other or prefer to self-describe (Please specify)

Thinking about your current (or last) main job or occupation. Do (did) you work as an employee or are (were) you self-employed?

- Prefer not to say [If ticked will automatically move to question about where you live]
- Never worked [If ticked will automatically move to question about where you live]
- Employee [If ticked will move to how many people work for your employer question]
- Self-employed with employees [If ticked will move to how many people you employ]
- Self-employed/freelance without employees [If ticked will move to question about description of work]

How many people work (worked) for your employer at the place where you work (worked)?

- Prefer not to say [If ticked will automatically move to question about where you live]
- 1-24 [If ticked will move to question about supervisory role]
- 25 or more [If ticked will move to question about supervisory role]

How many people do (did) you employ?

- Prefer not to say [If ticked will automatically move to question about where you live]
- 1-24
- 25 or more

Do (did) you supervise any other employees on a day to day basis?

• Prefer not to say [If ticked will automatically move to question about where you live]

- Yes
- No

And which best describes the work you do (did)?

- Prefer not to say
- Modern professional occupations such as: teacher nurse physiotherapist social worker welfare officer artist musician police office (sergeant or above) software designer
- Clerical and intermediate occupations such as: secretary personal assistant clerical worker - office clerk - call centre agent - nursing auxiliary - nursery nurse
- Senior managers or administrators (responsible for planning, organising, and co-coordinating work and for finance) such as: finance manager chief executive
- Technical and craft occupations such as: motor mechanic fitter inspector plumber printer tool maker electrician gardener train driver
- Semi-routine manual and service occupations such as: postal worker machine operative security guard caretaker farm worker catering assistant receptionist sales assistant
- Routine manual and service occupations such as: HGV driver van driver cleaner porter packer sewing machinist messenger labourer waiter/waitress bar staff
- Middle or junior managers such as: office manager retail manager bank manager restaurant manager warehouse manager publican
- Traditional professional occupations such as: accountant solicitor medical practitioner scientist civil/mechanical engineer

And where in the UK do you currently live?

- Prefer not to say
- England
- Northern Ireland
- Scotland
- Wales
- Channel Islands
- Isle of Man
- None of these

[If England ticked the following further options appear:

Prefer not to say, North East, North West, Yorkshire and Humber, West Midlands East Midlands, East of England, London, South East, South West, Other (Please specify)]

[If Scotland ticked the following further options appear: Prefer not to say, North Scotland, North East Scotland, East Scotland, West Scotland, South Scotland, Other (Please specify)]

We would like to know your postcode so that we can analyse our results by "geography", such as urban versus rural areas. You do not have to give this. However, if you do, we will never disclose it or identify you from it.

- I prefer not to give my postcode
- I am happy to give my postcode [If ticked box provided to type in postcode]

Before you submit your answers there is the option to leave an e-mail address should you wish to have the final report of the survey results personally e-mailed to you.

Please note: all e-mail addresses will be removed from the survey answers so that you cannot be identified and will be held securely on password-protected computers at the University of Cambridge until the results are available, as described in the information sheet at the start of the survey.

If you wish to leave an e-mail address, please do so in the box below and then submit your answers. Otherwise, please submit your answers now.

Optional

[Once submitted the following statement appears]

What happens next?

Once the survey has closed the results will be analysed by members of the CLIMB project team, colleagues at the University of Cambridge and their partners.

The study team hope the results of this survey can be used to inform and improve the way the NHS/HSC manage data for clinical and research purposes. Once a final report has been written it will be published on the research teams' websites at the following addresses:

https://www.climbproject.org.uk/ and https://www.psychiatry.cam.ac.uk/

You may wish to write these down. If you have left an email address the study team will email you with the results when they are available.

Thank you very much for taking part in this survey. We really appreciate your time.

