6.3 Analysis of Endpoints

The study team will collect data on people's preferences regarding data sharing using Likertstyle scales, yielding interval/ordinal data on preferences (e.g. "very unlikely to share"/"strongly disagree" through to "very likely to share"). For part of the survey, the team will superimpose a randomised intervention, namely a framing statement, prior to seeking views relating to the sharing of mental versus physical health data. The framing statement will be one of three: a "security" framing emphasising previous work reporting others' greater concerns about sharing mental health data versus other kinds of health data; a "neutral" statement; and a "holistic" framing emphasising the interrelationship between mental and physical illness.

The team will examine the distribution of response data and anticipate using general linear modelling when its assumptions are satisfied (e.g. normally distributed residuals) ²⁸ but non-parametric alternatives (e.g. Kruskall-Wallis H test) where they are not. They will use R ²⁶ for statistical analysis. Predictors to be examined include age range, gender, ethnicity, self-reported educational level, geographical indicators (NHS region of respondent, index of multiple deprivation), personal experience of relevant NHS services/disorders, and experimental manipulation (framing).

Primary measures will be the self-reported overall degree of support for: (a) sharing physical health data for NHS clinical care without explicit consent each time, and how far such sharing should extend; (b) likewise for mental health data; (c) sharing de-identified structured physical health data for research without explicit consent, and how far such sharing should extend (e.g. NHS, academic, charities, industry, publicly); (d) likewise for mental health data; (e) as for (c) but with de-identified free text data; (f) as for (d) but with de-identified free text data.

Secondary measures will include (g) the effect of the framing interventions; (h) the degree of support for a single national sign-up mechanism for sharing one's health data for clinical care

and/or research; (i) views on a prototype national NHS data sharing consent form; (j) views on trusted-third-party linkage between health data and a range of other UK state-held data sources (e.g. education, criminal justice).

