We would like to know/gauge your understanding of how NHS clinical care providers currently share your identifiable health data for your clinical care, without asking you each time. If you are not sure, please have a 'best guess' as to what you think might happen.

My understanding is that (please tick only one):

- My identifiable health data is currently shared freely between all NHS sites across the UK-i.e. all acute hospital Trusts, my GP, all mental health Trusts, ambulance service etc. in the whole UK
- My identifiable health data is currently shared between all NHS sites but only in the home nation that I live in -- i.e. shared only in England, or Scotland, or Northern Ireland, or Wales, but not between them
- My identifiable health data is currently only shared between all NHS sites in my region (cluster of hospitals nearest to your local hospital)
- My identifiable health data is currently only shared between my GP, acute local hospital, local mental health Trust and other local services
- My identifiable health data is currently not shared between any NHS sites

Q2.

MOST hospital Trusts, GPs, mental health Trusts are separate and currently DO NOT share identifiable health data without asking you, though they correspond and communicate with each other with your permission.

In view of the statement above, we would now like to ask you your views on sharing your own identifiable health data for YOUR CLINICAL CARE, without having to be asked each time (please tick only one):

- I would like my identifiable health data to be shared for clinical purposes with any part of the NHS in the UK, without asking me first
- I would like my identifiable health data to be shared for clinical purposes with any part of the NHS in my home nation only (i.e. only in England, or only in Northern Ireland, or only in Scotland, or only in Wales) without asking me first
- I would like my identifiable health data to be shared for clinical purposes with any part of my region (cluster of hospitals nearest to your local hospital), without asking me first
- I would like my identifiable health data to be shared for clinical purposes only with my GP, local hospital, and local mental health services, without asking me first
- No one in the NHS should share my identifiable health data without asking me first
- Not sure

We would now like to ask you some questions about your own PHYSICAL and MENTAL health. You can 'prefer not to say' if you wish.

Q3

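### Survey Q2 asks about sharing without being asked 'each time' but its answers say 'first', so literal readers content with one-off consent are pooled with those who want to be asked every time

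*Protocol*

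**What the plan says.** The lead-in to Q2 (Protocol, Appendix 3, Survey) tells respondents that most hospital Trusts, GPs and mental health Trusts "currently DO NOT share identifiable health data without asking you, though they correspond and communicate with each other with your permission". The stem then seeks views on "sharing your own identifiable health data for YOUR CLINICAL CARE, without having to be asked each time (please tick only one").

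There are six answers. The first four differ only in geographic reach (UK, home nation, region, local) and share one ending. The UK-wide version has data "shared for clinical purposes with any part of the NHS in the UK, without asking me first". The fifth answer is "No one in the NHS should share my identifiable health data without asking me first" and the sixth is 'Not sure'. There is no 'other' and no 'prefer not to say'.

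Three other places bear on the same idea:

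- Section 6.3 defines primary measure (a) as support for "sharing physical health data for NHS clinical care without explicit consent each time, and how far such sharing should extend", and measure (b) as the same for mental health data.
- Q5 (physical) and Q6 (mental) set the condition as not being asked every time. Their rows add no condition of their own.
- The text before Q15 describes the form proposed under objective 2.2(b): "By completing one consent form it would then be possible for all UK NHS professionals to access their patient's identifiable health data".

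**The concern.** Not being asked each time and not being asked first are different conditions. A person asked once, who then lets the data flow, meets the stem but not the sharing answers. Many respondents may hold that middle position, because it is the policy the study itself puts forward: the background complains of repeated consents, and the prototype form replaces them with one.

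At stake is what Q2 can be said to measure. It is the only preference item on identifiable clinical sharing asked before the framing statement (Q1 also comes before it, but asks about understanding). It is also the only tick-one item on how far respondents want such sharing to extend. If its answers test a stricter condition than its stem, a tabulation of Q2 against the primary objective will mix two views in one category.

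**Working it through.** **1. Figures in the plan.** No number in the protocol depends on Q2. The only power figure, 1,269 in section 6.1, is for a three-group comparison with f = 0.1 and power 0.9. It reproduces as a one-way ANOVA with noncentrality N × f² and alpha 0.05 (assumed; none is stated): power is 0.8999 at N = 1,268 and 0.9001 at N = 1,269. The point here leaves it untouched.

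**2. The condition, place by place.**

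| Place | Condition on asking |
|---|---|
| Q2 stem | not asked each time |
| Q2 answers 1 to 4 | not asked first |
| Q2 answer 5 | must be asked first |
| Primary measure (a), section 6.3 | no explicit consent each time |
| Q5 and Q6 | not asked every time |
| Form described before Q15 | asked once, then UK-wide access |

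Only the Q2 answers use 'first'.

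**3. Where each kind of respondent lands, reading literally.**

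| Respondent's view | Q2 as worded | Q2 with 'each time' in answers 1 to 5 | Q5/Q6 |
|---|---|---|---|
| No asking needed | 1 to 4 | 1 to 4 | can answer likely |
| Ask once, then share | 5 (or 'Not sure') | 1 to 4 | can answer likely |
| Ask every time | 5 | 5 | would answer unlikely |

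As worded, answer 5 holds two groups that Q5 and Q6 separate. One person can truthfully tick answer 5 in Q2 and 'Very Likely' on every row of Q5 and Q6. With the wording aligned, Q2 divides respondents at the same point as Q5, Q6 and measure (a).

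**4. Size.** Let q be the share who want exactly one-off consent, and r the fraction of them who read 'first' literally. Support for sharing without repeated asking is then understated in Q2 by q × r. The protocol gives neither value. Purely to show the range, with q assumed between 5% and 30%:

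- r = 0: no understatement, whatever q is.
- r = 0.5: 0.05 × 0.5 = 2.5 points, up to 0.30 × 0.5 = 15 points.
- r = 1: 5 points, up to 30 points.

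This is misclassification rather than sampling error, so the planned 20,000 responses would not reduce it.

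**5. Reach.** Q2 is answered before the framing statement is randomised, so any misreading is balanced across the three arms in expectation. The predictors listed in Study Design and Methods and in section 6.3 do not include Q2.

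**The case against.** The strongest reply is that the mismatch costs little.

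- Answer 5 is not a refusal. It is literally true of someone who wants to be asked once, and one-off consent is explicit consent. Asking versus not asking is also the contrast drawn in the lead-in and in the background on explicit and implicit consent. This stands: the fault is pooling, and it becomes a false count of opponents only if an analyst labels it so. The protocol fixes no such coding.
- Views on a one-off consent form are sought directly in Q11 to Q15, including overall likelihood of use (Q14) and whether the respondent would sign it today (last row of Q15). This stands, and is why Q2 needs no ask-once answer.
- Measures (a) and (b) separate physical from mental data. Q2 does not, whereas Q5 and Q6 do, with consistent wording. This stands: those measures can be obtained without Q2.
- Many respondents will carry 'each time' over from the stem and tick answers 1 to 4 as intended. This stands as a limit on size. It does not rescue the item, because a category whose meaning depends on the reader cannot be interpreted cleanly.

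What survives is that Q2's answers do not match its own question.

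**Conclusion.** The mismatch is in the current survey text. Q2 may understate support for sharing without repeated asking, and its results should not be set beside Q5 and Q6 as if they measured the same thing. The size cannot be given: it depends on how many respondents want one-off consent and how many read 'first' literally, and the documents give neither.

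A reader might infer three stronger things, none of which the documents support:

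- *That one-off-consent respondents are recorded as refusing to share.* Answer 5 is not worded as refusal.
- *That Q2 is a damaged baseline for the framing analysis.* The protocol never gives it that role, and because it precedes randomisation the misreading cannot bias the framing contrast.
- *That support is understated by some definite number of points.* Any such figure only restates an assumption.

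The problem is confined to one item and comparisons with it, but it bears on the primary objective and is nearly free to correct.

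**What to change.** Replace 'first' with 'each time' in all five substantive Q2 answers, so that the first four end 'without asking me each time' and the fifth says that no one should share without asking each time. Do not also add an ask-once answer. Once the wording is aligned, such a respondent already fits answers 1 to 4, so the extra answer would overlap with them on a tick-one item and would carry no geographic reach.

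Before launch the cost is rewording one item, with no extra participants. Appendix 3 gives a link to a live survey. If collection has begun, rewording would leave Q2 in two versions. In that case keep the wording, do not report answer 5 as opposition to sharing, and cross-tabulate it against Q5/Q6, Q14 and the last row of Q15 to show how many who ticked it would accept sharing without repeated asking or would sign the one-off form.
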